13. ALTERNATIVES TO STUDY PARTICIPATION

The alternative to participation in this study is to not participate and continue with any prior clinical care.

14. POTENTIAL RISKS

GENERAL ADVERSE EFFECTS

The risks and discomforts known to occur from the use of cannabis include but may not be limited to the following: coordination difficulties, dizziness, lightheadedness, eye irritation, increased heart rate (rapid heart beat), decreased blood pressure (low pressure of blood within arteries), sedation (sleepiness), feeling high, reversible effects on your appetite, mood, memory (ability or recall) and judgment (capacity to form an opinion). Specific mood changes may include anxiety, paranoia, and unusual, disturbing thoughts. Individual response to cannabis varies widely.

DEPENDENCE

Few Cannabis users develop dependence. With prolonged use, individuals may experience withdrawal symptoms such as irritability, restlessness, mild agitation, cramping, nausea, vomiting, sleep disturbances, and loss of appetite. Based on the dose of CBD and THC in TILRAY TN-CT120LM (FDA IND#137400), we do not anticipate symptoms of dependence or withdrawal, but will monitor for them nonetheless.

SOCIAL

Subjects are also informed that THC and CBD can be found in the body days or weeks after exposure, leading to a theoretical risk of a positive drug test should the subject be seeking employment, or undergoes testing as a part of their employment.

CARDIOVASCULAR

While the use of one of the cannabinoids (THC) found in the investigational drug is a rare trigger of cardiovascular events, there may be a significant increase in the rate of cardiovascular events (e.g. heart attack) for 1 hour following the use of cannabis.

REPRODUCTIVE RISKS

While THC and CBD are not known to cause birth defects, the investigators do not wish to expose the unborn child to any unnecessary medications, so subjects who are pregnant or unwilling to use a contraceptive during the course of the study will be excluded. A urine pregnancy test will be performed and confirmed negative before women of childbearing potential may participate in the study.

BLOOD SAMPLING

Since a blood sample will be collected at required study visits, subjects are informed about the risks of pain, discomfort, redness, bruising, infection and/or irritation at the needle insertion site, and rare risks of fainting, dizziness, and lightheadedness that may occur.

QUESTIONNAIRES AND SCALES

Subjects will need to complete questionnaires and scales during the study visits. These ask about quality of life and ability to carry out certain daily activities. Reviewing health related information might be stressful or make the subject feel uncomfortable.

LOSS OF CONFIDENTIALITY

Every effort will be made to keep all information including the results for substance abuse screening confidential; however there is slight risk of loss of confidentiality that may affect a subject's employability, insurability, ability to adopt and possible criminal/civil liabilities. These risks will be minimized to the extent possible.

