6. SPECIFIC AIMS

The present study seeks to assess the efficacy and tolerability of TILRAY TN-CT120LM (FDA IND#137400), a pharmaceutical-grade formulation containing THC and CBD, vs. placebo in an Essential Tremor patient population. The study is intended to collect pilot data to determine whether larger studies are warranted and assist in their future design.

Aim 1: To determine if short-term exposure to orally administered THC/CBD improves tremor amplitude in ET patients. Hypothesis 1: ET patients receiving THC/CBD orally will have reduced peak tremor power (compared with their own baseline measures) by accelerometry and spirography vs. placebo.

Aim 2: To determine acute and short-term tolerability of orally administered THC/CBD. Hypothesis 2: ET patients receiving THC/CBD orally will be associated with more frequent ratings of sedation on the Common Toxicity Criteria compared with placebo.

Aim 3: To characterize the relationship between THC/CBD exposure with clinical response (i.e. tremor amplitude) to define a plausibly useful dose range for evaluation in future confirmatory clinical trials.

BACKGROUND AND SIGNIFICANCE 7.

7.1 There is a great medical need for a more effective treatment for essential tremor.

Essential tremor (ET) is traditionally defined as bilateral, generally symmetric postural and kinetic tremor of the upper extremities that is not attributable to identifiable causes, and has been present for at least 5 years. A meta-analysis of prevalence studies indicates that 0.4 to 0.9% of the general population has ET. The figure rises to 4.6 to 6.3% among those 65 years or older (Louis and Ferreira, 2010). ET is a common cause of embarrassment, social withdrawal, disability, and loss of occupation.

The most commonly utilized medications for ET are propranolol, primidone, topiramate, gabapentin, and benzodiazepines. Unfortunately, the long-term efficacy and tolerability of current medications leave much to be desired. If one surveys hundreds of ET patients, it is found that one-third have stopped all ET medications, even those with the most severe tremor. In other words, many of the most disabled ET patients have abandoned the search for a drug that can help them. Over half the patients who try primidone, propranolol, diazepam or topiramate end up stopping them, and the percentage is higher with other anti-ET medications (Louis et al., 2010).

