The starting dose, titration schedule and target dose were selected based on safety, tolerability and efficacy data reported in previous studies using cannabinoids to treat pain (Langford et al., 2013; Portenoy et al., 2012; Johnson et al., 2010). Adverse effects will be inventoried at each study visit. If the patient or investigator feel that the higher study drug dose is causing troublesome side effects, the dosage may be lowered. Food intake can affect systemic exposure of cannabinoids (Zgair et al. 2016). Subjects will be advised to schedule their dose at a similar time every morning after breakfast to maintain similar systemic exposure throughout the study. Regular reminders will be provided to subjects to ensure they are taking the study drug post-meals. During study visits when drug is administered, subjects will be provided with a standardized FDA high-fat, high-calorie meal prior to taking the study drug.

DOSE TAPER AND WASHOUT

After completing a 2-week course on 15/300 mg/day of THC/CBD or placebo, subjects will return on this dose for assessment and completion of the various measures detailed in Appendix 1. After completion of this visit, subjects will taper from the treatment gradually over 1-week, in similar fashion to the dose titration up to the target dose. Subjects will then complete a 3-week washout period prior to being crossed-over to the alternate arm. This is to allow subjects to return to their baselines. The duration selected is conservative and takes into consideration the known elimination half-life of THC/CBD.

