This is a standardized and commonly used 7-point scale in which both the subject (PGI) and blinded clinician (CGI) rate the degree of change from baseline.

PATIENT REPORTED OUTCOMES OF THE COMMON TERMINOLOGY CRITERIA

All adverse events will be assessed and recorded using the Patient Reported Outcomes of the Common Terminology Criteria for Adverse Events (PRO-CTCAE) version 1.0. This is a standardized tool for identifying adverse events across all organ systems and includes severity classification.

PHARMACOKINETIC ANALYSES

Established nonlinear mixed-effects modeling methods will be used to evaluate the population pharmacokinetic and pharmacodynamic properties of CBD, THC, and 11-OH-THC. The correlation between plasma concentrations and/or PK parameters with demographic factors (age, sex, body size, race) will be investigated, along with analysis of any relationship between exposure and the resulting efficacy and/or safety response. Different relationships (linear, log-linear, Emax and Sigmoidal Emax) will be explored to correlate exposure with pharmacodynamic metrics (assessment measures of tremor). In addition, as prior studies have shown a hysteresis between THC plasma concentration and drug effect, we anticipate modeling the effect(s) using a hypothetical effect compartment, i.e. $dCe/dt = ke0 \cdot (Cp - Ce)$, where Cp is the plasma concentration, Ce is the concentration in the effect compartment, and ke0 is the a first-order rate constant describing transport into the effect compartment. The final population pharmacokinetic model will be used to perform Monte Carlo simulations to determine the distribution of CBD, THC, and 11-OH-THC at various oral doses.

COLUMBIA-SUICIDE SEVERITY RATING SCALE (C-SSRS)

Suicidality will be assessed by trained study personnel using the C-SSRS (Posner et al. 2011). The C-SSRS is a standardized suicidal rating system conducted by a certified rater. The interview measures presence of suicidality and consists of four categories: suicide ideation, intensity of ideation, suicidal behavior and answer

for actual attempts only. This scale will be used for screening as well as to assess for the occurrence of any suicidal ideation and/or behavior during the study.

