APPENDIX 1: STUDY OVERVIEW

EVENT	VISIT 0: SCREENING	VISIT 1: DOSE TITRATION	VISIT 2: PK	VISIT 3: PK	TREATMENT PHASE	VISIT 4: ASSESSMENT	TAPER	WASHOUT	VISIT 5: DOSE TITRATION	VISIT 6: PK	VISIT 7: PK	TREATMENT PHASE	VISIT 8: ASSESSMENT	TAPER	TELEPHONE FOLLOW-UP	TOTAL DAYS
TOTAL DAYS	0	ų	5	1	16	1	5	22	ų	5	1	16	1	5	1	77
DAY NUMBER (±3)	0	1	3	6		22	23	28	50	52	55		71	72	77	
Consent	х															
Neurological Exam	х					x							х			
Vital Signs	х	х	Х	x		х			х	х	x		х			
TETRAS (video)	х					х							х			
Spirography	Х					X							Х			
Accelerometry	Х					Х							Х			
CGI/PGI						Х							Х			
PRO-CTCAE	х	x	х	x		х			x	х	x		х		х	
C-SSRS	Х					Х							Х		Х	
Lab Testing - pregnancy, CBC, CMP, Drug screen	x					x							x			
EKG*	x	x	x	x		x			x	x	x		x			
PK Sample(s)			Х	x		X				x	х		х			

* EKG at screening, then post-dose at each subsequent visit.

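### No contact is scheduled after the first taper, although withdrawal is to be monitored and the second taper ends with a telephone safety call

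*Combined protocol and SAP*

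**What the plan says.** - **Commitment.** Section 14 (Dependence) lists possible withdrawal symptoms and then says "we do not anticipate symptoms of dependence or withdrawal, but will monitor for them nonetheless".
- **End of each period.** Section 9.3 says that after the assessment visit "subjects will taper from the treatment gradually over 1-week". It continues: "Subjects will then complete a 3-week washout period prior to being crossed-over to the alternate arm".
- **Schedule.** In Appendix 1 the first Taper column (from day 23) and the Washout column (from day 28) are empty in every procedure row. The next contact is Visit 5 on day 50, the first dosing visit of the second period. After the second taper there is a column headed "TELEPHONE FOLLOW-UP" on day 77, marked for PRO-CTCAE and C-SSRS.
- **Instruments.** PRO-CTCAE is marked at every visit from screening to Visit 8. C-SSRS is marked at screening, Visit 4, Visit 8 and the day-77 call, but not at Visit 5.
- **Recording of events.** Section 9.3: "Adverse effects will be inventoried at each study visit". Section 9.4: "All adverse events will be assessed and recorded using the Patient Reported Outcomes of the Common Terminology Criteria for Adverse Events". The plan gives no recall window, no rule assigning taper or washout events to a treatment, and no statement on whether the Visit 5 PRO-CTCAE comes before or after the dose.
- **Tolerability aim.** Aim 2 reads "To determine acute and short-term tolerability of orally administered THC/CBD". Its hypothesis is that active treatment "will be associated with more frequent ratings of sedation on the Common Toxicity Criteria compared with placebo".

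**The concern.** In a two-period cross-over, each subject stops active drug once: after Period 1 if active came first, after Period 2 if placebo came first. Only the second stop is followed by a scheduled contact. Whether a subject is promptly asked about symptoms after stopping active drug is thus decided by the randomised sequence.

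Two things are at stake. The first is safety information: the plan says it will monitor for withdrawal, and for active-first subjects nothing scheduled does so near the taper. The C-SSRS gap is longer still. The second is comparability: any summary of symptoms after stopping drug against symptoms after stopping placebo would rest on unequal capture. For active-first subjects, late reports would also surface at the first visit of the placebo period, with no rule saying where they belong. This is a pilot meant to guide larger studies, so a clean description of after-effects has some value.

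**Working it through.** **1. Days (inputs: Appendix 1).** The appendix is internally consistent: 23 + 5 = 28, 28 + 22 = 50, 72 + 5 = 77.

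| Interval | After Period 1 | After Period 2 |
|---|---|---|
| Assessment visit to next scheduled contact | 50 − 22 = 28 days | 77 − 71 = 6 days |
| Scheduled end of taper to that contact | 50 − 28 = 22 days | 77 − 77 = 0 days |
| C-SSRS to next C-SSRS | 71 − 22 = 49 days | 77 − 71 = 6 days |

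With ±3 days at each end, the 28-day gap runs from 28 − 6 = 22 to 28 + 6 = 34 days.

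**2. Subjects concerned.** Sections 9.7 and 10.1 plan 16 completers. The allocation ratio is not stated; 1:1 is assumed, giving 8 active-first subjects. So 8 of 16 active tapers end without a scheduled contact.

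**3. On-treatment comparison.** PRO-CTCAE falls on days 1, 3, 6 and 22 in Period 1 and on days 50, 52, 55 and 71 in Period 2. Subtracting 49 from the second set gives 1, 3, 6 and 22. The schedules match exactly, so a comparison of Visits 1–4 with Visits 5–8 loses nothing from the missing call.

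**4. Comparison of after-effects, if made.** The plan gives no rates, so these are assumptions. Let pa and pb be the after-effect rates following active and placebo, and w the share of placebo-first subjects. Full capture gives pa − pb. If first-taper events are never recorded but all subjects stay in the denominator, the expected difference is w·pa − (1 − w)·pb.

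| pa / pb (assumed) | Full capture | w = 0.5 | w = 0.4 | w = 0.6 |
|---|---|---|---|---|
| 0.10 / 0.05 | 0.05 | 0.025 (50%) | 0.01 (20%) | 0.04 (80%) |
| 0.25 / 0.10 | 0.15 | 0.075 (50%) | 0.04 (27%) | 0.11 (73%) |
| 0.40 / 0.10 | 0.30 | 0.15 (50%) | 0.10 (33%) | 0.20 (67%) |

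Now let a share r of first-taper events be recalled at Visit 5, with w = 0.5:
- Assigned by onset date to the preceding treatment: (pa − pb)(1 + r)/2, from half at r = 0 to the full difference at r = 1.
- Counted to Period 2: (pa − pb)(1 − r)/2, from half at r = 0 to zero at r = 1.

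For 0.25 / 0.10, the first rule gives 7.5 to 15 points and the second 7.5 down to 0.

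**5. Expected counts.** At pa = 0.25, 16 × 0.25 = 4 subjects would have symptoms after active drug, and 8 × 0.25 = 2 of them would be active-first. At 0.10 the figures are 1.6 and 0.8; at 0.40 they are 6.4 and 3.2.

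**The case against.** A reader might infer that the Aim 2 drug-placebo tolerability difference is diluted, or that at most half of it can be recovered. The documents do not support either. The Aim 2 hypothesis concerns sedation, an effect of exposure that is not among the withdrawal symptoms in Section 14, and the on-treatment assessments are symmetric. No section puts taper or washout symptoms into the drug-placebo comparison, and Section 9.8 gives no method for adverse events. A ceiling of one half needs equal sequences and Visit 5 reports counted to Period 2, and the plan states neither. Assignment by onset date gives half to all of the difference. A comparison confined to the second taper would not be biased by the gap either, though it would be between subjects and use half of the tapers.

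Nor can one say that the events are missed. PRO-CTCAE is marked at Visit 5, the consent form gives a study contact (Section 12), and Section 15 foresees telephone reports between visits, though only of suicidal ideation. The accurate statement is that no contact is *scheduled*.

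Three further points count against giving this much weight. The plan does not expect withdrawal at this dose. Expected counts are small, and the primary outcome, spirography, is untouched. The day-77 call comes at the scheduled end of the taper, so placebo-first subjects have no later follow-up either. In addition, the Appendix 2 chart is not in the text available, so any contact noted there could not be checked.

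All of this stands, and it limits the point. It does not explain why a call is planned after one taper and not the other, or how the Section 14 commitment is met for active-first subjects.

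**Conclusion.** The gap and its asymmetry are established from Appendix 1: 28 days without scheduled contact after Period 1 (22 to 34 with the windows) against 6 after Period 2, and 49 against 6 days between C-SSRS assessments. If the sequences are equal, about half of the active tapers have no scheduled check near their end, which falls short of what Section 14 says will be done.

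The effect on inference is conditional. On-treatment tolerability and the sedation hypothesis are unaffected. A comparison of after-effects, if one is made, may be understated; the amount depends on the unstated allocation ratio, on recall and on the missing assignment rule, and every rate used above is assumed. The point is minor, and worth acting on because the remedy is cheap.

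**What to change.** 1. Add to Appendix 1, at the end of the first taper (about day 28), the same telephone PRO-CTCAE and C-SSRS contact that is planned for day 77. The interval from the assessment visit is then 6 days in both periods (28 − 22 and 77 − 71), and 22 days remain to Visit 5.
2. State that the Visit 5 PRO-CTCAE is taken before dosing, and that taper and washout events are assigned by onset date to the preceding treatment.
3. Say in Section 9.8 that any comparison of after-effects uses the two matched post-taper calls.
4. Reconcile the taper and washout lengths in Section 9.3 (1 week and 3 weeks) with Appendix 1 (5 and 22 days). Seven days from day 23 or day 72 would run through day 29 or day 78, so each call should be tied to the actual end of the taper.

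The cost is one short call per subject, at most 20 in all, plus a few lines of text. Only data collection and attribution change.

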15. RISK MANAGEMENT PROCEDURES AND ADEQUACY OF RESOURCES

Subject safety and tolerability will be monitored in this study across multiple dimensions by tracking clinical adverse events; vital signs (including orthostatic pulse and blood pressure); general and neurological physical examinations; standard clinical laboratory safety panels for complete blood counts, chemistry, coagulation, and urinalysis; standard 12-lead electrocardiograms; the Patient Reported Outcomes of the Common Terminology Criteria for Adverse Events (PRO-CTCAE), and Columbia Suicide Severity Rating Scale (C-SSRS). Subjects answering "yes" to Suicidal Ideation item 4 or 5 on the C-SSRS during the study must be withdrawn from the study treatment. The PI will also withdraw subjects from treatment if, in the judgment of the Investigator, the subject develops other indicators of significant risk of suicide. In the event that suicidal ideation is observed in any study subject, the PI will manage the situation as he/she deems medically and psychiatrically appropriate. Further, In the event that a subject reports suicidal ideation, the subject will be withdrawn from the study and personally escorted by a study team member to the UCSD Emergency department for urgent psychiatric evaluation and management. In the event that we are made aware of such suicidal ideation by telephone outside of routine study visits, subjects will be referred to a local ED for evaluation and we will conduct a telephone follow up to ensure the subject followed through with these recommendations.

The specified inclusion/exclusion criteria have been carefully considered to avoid enrollment of subjects for whom exposure to the study drug might pose a hazard, particularly as it relates to individuals with a history of substance abuse.

In order to provide independent oversight over patient safety, the PI will select of committee of up to 4 qualified individuals to serve on a Data Safety and Monitoring Board (DSMB). The DSMB will receive regular updates (minimum of quarterly) on adverse events and will have access to unblinded data should they decide to explore whether a frequent or serious adverse event is associated with the study drug. All serious adverse events (SAEs) meeting criteria for expedited reporting to the US FDA will be reported to the FDA, IRB, and DSMB in accordance with regulatory timelines. In the case of a fatal or life-threatening event, we will notify the FDA by telephone within 3 working days and stop further enrollment until the serious adverse event can be reviewed by the DSMB. In addition, any event that is unexpected will be reported to the FDA and IRB within 7 working days.

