9.3 Description of Screening and Study Design

SCREENING VISIT

After being screened for inclusion/exclusion criteria and providing informed consent, subjects will undergo a complete neurological examination to confirm their diagnosis of ET and exclude other neurological disorders. Additional measures collected during this visit are listed in Appendix 1. Note that subjects will need to have been on a stable dose of their medications for a minimum of 6 weeks prior to the screening visit and will be

encouraged to remain on these doses for the remainder of the study period. Subjects will be asked about their other tremor medication doses at each follow-up visit to confirm stable doses.

VIDEOTAPED TETRAS

As part of each study visit (1-3), subjects will complete a TETRAS rating scale while being videotaped. This is intended for rating purposes by two blinded raters at the completion of the study.

RANDOMIZATION

After completion of the screening visit, subjects will be assigned to one of two possible treatment arms based on a pre-set randomization matrix. Only the research pharmacy who will be responsible for dispensing the doses will be aware of which of two treatment options will be provided, but not the identity of the particular agent. The equivalence of the THC/CBD and Placebo will be equally matched by the manufacturer, making it difficult for the subject to discriminate which arm they are on. Subjects will be asked which arm they are receiving at each assessment visit and on telephone follow up to assess for potential unblinding.

DOSE TITRATION AND TREATMENT

On visit 1 and 5, subjects will receive 1 capsule of IMP every morning. On visit 2 and/or 6, if the subject tolerated 1 capsule then they would receive 2 capsules every morning. Alternatively, if 1 capsule was not tolerated, the timing of the administration would be changed to 1 capsule in the evening. At visit 3 and/or 7, if the single nightly capsule was not tolerated, the subject would be dropped at this visit. If the 2 capsules every morning were tolerated, the subject would then receive 2 capsules in the morning and 1 capsule in the evening. If 2 capsules in the morning were not tolerated, the subject dosing would be changed to 1 capsule in the morning and 1 capsule in the morning and 1 capsule nightly. Subjects will remain on the highest tolerable dose for the duration of the period until visit 4 or 8 (See Appendix 2).

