10.2 Inclusion/Exclusion Criteria

Inclusion criteria

- Subjects with ET diagnosed by a Movement Disorder Neurologist aged 21 and older
- Subjects on a stable dose of tremor medication for a period of at least 6 weeks prior to screening
- Subjects with upper limb tremors
- Subjects with a minimum score of 2 on the TETRAS Question 2.4 (amplitude of at least 1-3cm)

Exclusion criteria

- Subjects with significant non-ET related abnormal findings on neurological exam.
- Subjects with a tremor at rest.
- Subjects with a diagnosis of mild cognitive impairment or dementia
- Subjects who are pregnant or nursing, or suspect that they might be
- Women of childbearing potential unable or unwilling to use a form of contraception during course of the trial
- Subjects on medications known to interact with cannabinoid-type agents
- Subjects with a history of alcohol use disorder (based on DSM-5 criteria) or substance abuse.
- Subjects with exposure within the past 21 days to primidone or within the past 7 days to benzodiazepines, ketoconazole, ritonavir, clarithromycin, rifampin, carbamazepine, St. Johns Wort, digoxin or other agents known to be strong inducers or inhibitors of CYP3A, CYP2C19, and CYP2C9.
- Subjects unwilling to abstain from consumption of grapefruits, grapefruit juice or grapefruiting-containing products that are known to strongly inhibit CYP3A4.
- Subjects taking concomitant medications that are highly protein-bound with a narrow therapeutic index (e.g. warfarin, cyclosporine, and amphotericin B).
- Subjects who do not wish to take a cannabis-derived agent
- Subjects who an allergy or sensitivity to sorbitol, xylitol, stevia or other natural sweeteners
- Subjects with an allergy or sensitivity to cannabis.
- Subjects actively using cannabis or a cannabis-derived product (within 4 weeks of screening) or who are unwilling to discontinue its use during the course of the study.
- Subject with a history of significant Axis I psychiatric disorder (e.g., mania, bipolar depressive disorder, schizophrenia, schizoaffective disorder, or other major psychiatric disorder)
- Subject with active or prior history of suicidal ideation and/or behavior.
- Subject with significant coagulopathy, immunologic, gastrointestinal, respiratory, cardiovascular (e.g., uncontrolled hypertension, myocardial infarction in the last 18 months, significant bundle branch block, congestive heart disease), or endocrine (e.g., uncontrolled diabetes, hyperthyroidism) disorder

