9.16.3 APPENDIX 3: PHARMACOKINETIC SAMPLING TIMES**

DAY #	TIME
3	Trough
6	Trough
22	Trough + Pseudorandom (1,2,3,
	or 4 hrs/post-dose) sample

**NOTE: Samples will be collected for drug and placebo to maintain blinding, but PK lab will be unblinded in order to process only drug samples. If subject receive placebo first, PK days will be: #52, 55, and 71.

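### Minor, cheap improvement: repeat the C-SSRS at Visit 5 before dosing, because period 2 now starts on a suicidality check nominally 28 days old

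*Combined protocol and SAP*

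**What the plan says.** **The withdrawal rules.** Section 15 has three. A yes to ideation "item 4 or 5 on the C-SSRS during the study must be withdrawn from the study treatment". The investigator may also withdraw a subject on clinical judgment of suicide risk. The third is broader: "In the event that a subject reports suicidal ideation, the subject will be withdrawn from the study". Ideation learned of by telephone between visits is covered as well.

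**Eligibility.** Section 10.2 excludes a "Subject with active or prior history of suicidal ideation and/or behavior".

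**The schedule.** The C-SSRS row of Appendix 1 is marked at Visit 0 (day 0), Visit 4 (day 22), Visit 8 (day 71) and the telephone follow-up (day 77). The column "VISIT 5: DOSE TITRATION" (day 50) is marked for vital signs, PRO-CTCAE and EKG, but not for the C-SSRS.

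**What happens at Visit 5.** Section 9.3 restarts dosing there: "On visit 1 and 5, subjects will receive 1 capsule of IMP every morning". Before it come the taper and then the washout: "Subjects will then complete a 3-week washout period prior to being crossed-over to the alternate arm". The same section adds a general safeguard: "Adverse effects will be inventoried at each study visit".

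Section 9.4 gives the scale two uses, screening and detection during the study, and requires a certified rater. Neither 9.4 nor 9.5 adds an administration at Visit 5.

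**The concern.** A rule that withdraws a subject on a C-SSRS answer can act only when the C-SSRS is asked. Of the scheduled administrations after screening, day 22 is the only one that comes before a further full treatment period. Nearly four weeks of taper and washout then pass before that period begins, with no repeat.

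The two period starts are therefore unequal. Ideation bars entry, and the scale is given close to the first capsule of period 1. Period 2 has no matching check.

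This matters most in the placebo-first sequence. For these subjects the active drug begins at Visit 5, as Appendix 3 reflects: "If subject receive placebo first, PK days will be: #52, 55, and 71". If ideation has arisen since day 22 and the subject has not mentioned it, THC/CBD would be started in someone who would not meet the entry criterion if it were applied again.

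**Working it through.** **Inputs** (Appendix 1, day-number row): Visit 0 = 0, Visit 1 = 1, Visit 4 = 22, taper starts 23, washout starts 28, Visit 5 = 50, Visit 8 = 71, final call = 77; window ±3 days. The duration row is partly garbled in the extracted text, so only its legible taper (5) and washout (22) entries are used.

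**Is the missing mark real?** The C-SSRS row has the same number of cells as the PRO-CTCAE, vital signs and EKG rows. Those three rows do carry a mark at Visit 5, so the gap is not a reading artefact.

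**Reproducing day 50.**
- Appendix 1: 22 + 1 visit day + 5 taper days + 22 washout days = 50.
- Section 9.3: 22 + 7 (one-week taper) + 21 (three-week washout) = 50.

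**Age of the last C-SSRS at first dose.**
- Period 2: 50 − 22 = 28 days. With windows: (50 − 3) − (22 + 3) = 22, to (50 + 3) − (22 − 3) = 34.
- Period 1: 1 − 0 = 1 day. If only Visit 1 moves, at most 1 + 3 = 4. If both visits move, at most 1 + 3 + 3 = 7. It cannot be below 0, because screening comes first.

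The windows narrow the contrast but do not remove it: 22 to 34 days against 0 to 7.

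**Intervals between scheduled administrations.**

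| Schedule | C-SSRS days | Gaps (days) |
|---|---|---|
| Current | 0, 22, 71, 77 | 22, 49, 6 |
| With Visit 5 | 0, 22, 50, 71, 77 | 22, 28, 21, 6 |

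The longest gap falls from 49 to 28 days, and what remains of it is taper and washout.

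**What does not change.** From first dose to the next C-SSRS: period 1, 22 − 1 = 21 days; period 2, 71 − 50 = 21 days. Both are the same with or without the added mark.

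**Who gains, by sequence.**
- Placebo-first: no active drug has been taken by day 50. A check before dosing can stop THC/CBD from being started.
- Active-first: Visit 5 starts placebo. Holding the dose prevents no further THC/CBD exposure, so the gain is earlier detection.

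**Subjects affected.** Sections 9.7 and 10.1 plan 16 subjects with a ceiling of 20, and section 8 reports on the first five enrolled. If enrolment stands at five when the change is made, it reaches 16 − 5 = 11 to 20 − 5 = 15 later enrollees, plus any of the five still to reach Visit 5.

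**The case against.** The strongest reply is that the plan already has a wider rule than item 4 or 5. Any reported ideation leads to withdrawal and urgent evaluation, with no scheduled C-SSRS needed. Visit 5 is in person, adverse effects are inventoried, PRO-CTCAE is completed, and the investigator can withdraw on judgment. Entry excludes anyone with a history of ideation or behaviour, so few events are to be expected in 16 to 20 subjects. This stands. It reduces the gap to ideation that a structured interview would bring out and ordinary contact at Visit 5 would not.

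A reader might infer four stronger things, none of which the documents support:

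- **That the plan breaks its own safety rule.** It does not. The stated uses of the scale are screening and detection during the study, and the schedule provides both.
- **That the added check guards against mood effects of the drug.** Section 14 lists anxiety, paranoia and disturbing thoughts, but a check before the first period 2 capsule comes before that exposure in placebo-first subjects. In active-first subjects it comes after THC/CBD has ended.
- **That cover on treatment improves because the longest gap falls from 49 to 28 days.** The 21-day stretch from first dose is untouched.
- **That the C-SSRS at day 77, with none after the first washout, shows an inconsistency.** Day 77 is the last study contact and is by telephone; after period 1 the subject returns in person. Different contacts may reasonably carry different assessments.

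**Conclusion.** The observation is correct and the improvement is worth making, but it is minor. Period 2 dosing begins on a C-SSRS nominally 28 days old (22 to 34), against 1 day nominal and a few days at most in period 1. The unmet need is narrow: unreported ideation that arises during taper or washout, with the protective benefit mainly in one of the two sequences. The documents give no event rate and none is assumed; the case rests on the low cost of the check. It also assumes that the scale is completed before the first capsule at Visit 5. Given afterwards, it would not serve the purpose.

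**What to change.** In Appendix 1, mark the C-SSRS at Visit 5, covering the time since the last visit. State that it is completed before the first period 2 dose and that the item 4/5 rule is applied before study drug is dispensed.

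The cost is one interview for each subject who has not yet reached Visit 5, and a certified rater available at that visit. The instrument and raters are already in the study and the visit is already attended. The documents give no interview length. At an assumed 5 to 10 minutes, the later enrollees need 11 × 5 = 55 to 15 × 10 = 150 minutes in all, and each of the first five still to reach Visit 5 adds 5 to 10 minutes. Visit dates, endpoints, blinding and sample size do not change.

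If the sponsor also wants to shorten the 21 days on treatment without a C-SSRS, that needs extra contacts within each period and should be decided and costed separately.
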